AE=adverse event; BID=twice daily; BP=blood pressure; CBD=cannabidiol; C-SSRS=Columbia-Suicide Severity Rating Scale; D=Day; ECG=electrocardiogram; h=hour; HR=heart rate; PK=pharmacokinetic; PSL=Padsevonil; RR=respiratory rate; SEM=Saccadic Eye Movements; T=body temperature; VAS=Visual Analog Scale

Note: A washout of at least 4 days will occur between Treatment Periods 4 and 5 for PSL.

^a Prior to PSL/placebo/CBD administration.

^b Prior to and 2.5 hours after IMP administration.

^c CBD maintenance 10mg/kg BID (dose to be confirmed from CBD PK exposure in Treatment Period 1) between Treatment Period 4 and Treatment Period 5 for 4 Days (study participants in house).

^d D1: PSL 100mg BID; D2: PSL 200mg BID; D3: PSL 200mg BID; D4: PSL 200mg BID; D5: PSL 200mg AM; D5: PSL 100mg PM; D6: PSL 100mg BID; D7: PSL 100mg BID.

-
- ^f Blood samples for measurement of plasma concentration of PSL and CBD will be obtained at the following times: predose (within 5 minutes of dosing), and at Day 5 (PK day) postdose at 0.25h, 0.5h, 1h, 1.5h, 2h, 3h, 4h, 6h, 8h, and 12h postdose.
- ^g “Since Last Visit” version of the C-SSRS will be completed.
- ^h NeuroCart assessments in Part B consist of the following tests: Body Sway, VAS mood & alertness (Bond & Lader), VAS feeling high, internal- and external perception (Bowdle), SEM, and Smooth Pursuit Eye Movements. NeuroCarts assessments are taken twice at least 30 minutes prior to dosing and singlicate postdose at 30 minutes, 1, 2, 3, 4, 5, 6, 8, and 10 hours.
- ⁱ Urine samples for additional PK analysis will be collected 12-hours postdose on Day 5.

Table 1-9: Assessment schedule Part B: Treatment Period 6 and SFU

Study Period	Treatment Period 6						SFU Visit ^a
	D1	D2	D3	D4	D5	D6/D7	
Adverse events	X	X	X	X	X	X	X
Previous/concomitant meds	X	X	X	X	X	X	X
Hem/chem/urine ^b						X	X
Supine vital signs (BP, RR, HR, T) ^c	X		X			X ^d	X
Psychiatric and mental status	X		X			X	X
Triplicate 12-lead ECG ^c	X		X			X ^d	X
C-SSRS ^e	X					X ^d	X
CBD administration ^f	X	X		X	X	X	
CBD PK trough sampling ^b	X		X			X	X
Physical examination ^g	X		X			X ^d	X
Pregnancy test						X ^h	
Discharge	X					X ^d	

AE=adverse event; BID=twice daily; BP=blood pressure; CBD=cannabidiol; C-SSRS=Columbia-Suicide Severity Rating Scale; D=Day; ECG=electrocardiogram; h=hour; HR=heart rate; PK=pharmacokinetic; PSL=Padsevonil; RR=respiratory rate; SAE=serious adverse event; T=body temperature; VAS=Visual Analog Scale; W=Week

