3.6 Treatment assignment and treatment groups

3.6.1 Part A

For all analyses (where applicable) the results will be presented by phase and treatment. For summary tables, results from Treatment Period 3 and 6 will be presented by PSL. Sequence in full will be used where applicable (defined in [Section 2.2.2](#)).

Phase, phase day, treatment (for listings and tables) and the corresponding treatment period and day from the protocol are defined in Table 3-2.

Table 3–2: Definition of Phase - Part A

Protocol Treatment Period	Protocol Treatment Period Day	Phase	Phase Day	Treatment for Listings	Treatment for Tables
Screening	-28 to -2	Screening	-28 to -2	N/A	N/A
1	-1 to 2	Ethanol Phase	-1 to 2	Ethanol/Placebo	Ethanol/Placebo
2	1 to 2	Ethanol Phase	3 to 4	Ethanol/Placebo	Ethanol/Placebo
Washout Period	-	Ethanol Phase	5 to 6	Ethanol/Placebo	Ethanol/Placebo
3	-1	Interaction Phase	-1	Ethanol/Placebo	Ethanol/Placebo*
3	1	Interaction Phase	1	PSL up-titration	PSL
3	2 to 4	Interaction Phase	2 to 4	PSL maintenance	PSL
4	5	Interaction Phase	5	PSL+Ethanol/PSL+Placebo	PSL+Ethanol/PSL+Placebo
4	6	Interaction Phase	6	PSL maintenance	PSL
5	7	Interaction Phase	7	PSL+Ethanol/PSL+Placebo	PSL+Ethanol/PSL+Placebo
5	8	Interaction Phase	8	PSL tapering	PSL
6	9 to 10	Interaction Phase	9 to 10	PSL tapering	PSL
Follow-up	-	Follow-up	17 or 20	N/A	N/A

- = Day not specified in protocol; * If assessments are summarized by treatment, phase and day, then data will be presented as: PSL, Interaction Phase, Day -1. If assessments are summarized by treatment, then data from Day -1 will attribute to either Ethanol or Placebo e.g. if an AE occurs on Day -1, then the AE will be summarized where treatment is Ethanol or Placebo since this is the most recent treatment received.

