3.6.2 Part B

For all analyses (where applicable) the results will be presented by phase and treatment. For summary tables, results from Treatment Period 3 and 6 will be presented by CBD. Listings will also include phase day. Sequence in full will be used where applicable (defined in [Section 2.2.3](#)).

Phase, phase day, treatment (for listings and tables) and the corresponding treatment period and day from the protocol are defined in Table 3-3.

This document cannot be used to support any marketing authorization application and any extensions or variations thereof.

REDACTED COPY

Table 3–3: Definition of Phase - Part B

Protocol Treatment Period	Protocol Treatment Period Day	Phase	Phase Day	Treatment for Listings	Treatment for Tables
Screening	-28 to -2	Screening	-28 to -2	N/A	N/A
1	-1 to 2 (optional 15-16)	CBD Phase	-1 to 2 (optional 15-16)	CBD SD	CBD
Washout Period	-	CBD Phase	3 to 8 (or 17 to 22)	CBD SD	CBD
2	-1	PSL Phase	-1	CBD SD	CBD ^a
2	1 to 8	PSL Phase	1 to 8	PSL	PSL
Washout Period	-	PSL Phase	9 to 14	PSL	PSL
3	-1	Interaction Phase	-1	PSL	PSL ^b
3	1 to 16	Interaction Phase	1 to 16	CBD up-titration	CBD
4	1 to 7	Interaction Phase	17 to 23	CBD+PSL/CBD+Placebo	CBD+PSL/CBD+Placebo
CBD Dose Maintenance	-	Interaction Phase	24 to 27 ^c	CBD maintenance	CBD
5	1 to 7	Interaction Phase	28 to 34	CBD+PSL/CBD+Placebo	CBD+PSL/CBD+Placebo

Protocol Treatment Period	Protocol Treatment Period Day	Phase	Phase Day	Treatment for Listings	Treatment for Tables
6	1 to 7	Interaction Phase	35 to 41	CBD tapering	CBD
Follow-up	-	Follow-up	47 or 50	N/A	N/A

- = Day not specified in protocol; ^a If assessments are summarized by treatment, phase and day, then data will be presented as: PSL, PSL Phase, Day -1. If assessments are summarized by treatment, then data from Day -1 will attribute to CBD. ^b If assessments are summarized by treatment, phase and day, then data will be presented as: CBD, Interaction Phase, Day -1. If assessments are summarized by treatment, then data from Day -1 will attribute to PSL. ^c CBD dose maintenance will occur for at least 4 days. If dosing is maintained for more than 4 days, the phase day will need to be changed accordingly;

REDACTED COPY
 This document cannot be used to support any marketing authorization application or any extensions or variations thereof.

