11.1 Extent of exposure

Administration of treatments will be listed by study participant. For PSL and CBD, the listing will include the date and time of administration of the morning and evening dose, and total daily dose. For ethanol infusion, the listing will include the date of infusion, start and stop time of infusion, duration of infusion and total volume of ethanol given.

Exposure data will be listed only.

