11.2 Adverse events

All AEs will be coded using the MedDRA® and characterized as pre-treatment and treatment emergent according to the intake of each treatment. Adverse events with a start date prior to the first dose of treatment will be defined as pre-treatment AEs. A treatment-emergent AE (TEAE) is defined as any AE with a start date/time on or after the first dose of treatment or any unresolved event already present before administration of treatment that worsens in intensity following exposure to the treatment.

Adverse events will be attributed to the most recent treatment received. Adverse events that occur during the washout periods will be assigned as treatment emergent with regards to the treatment of the previous period.

The number and percentage of participants who experience TEAEs will be summarized by MedDRA SOC, PT and treatment.

Summaries of TEAEs will include the following:

- Incidence of overall TEAEs (overview including number and percentage of study participants with any TEAEs, serious TEAEs, discontinuations due to TEAEs, drug-related TEAEs, severe TEAEs and TEAEs leading to death; event counts will also be included)
- Incidence of TEAEs
- Incidence of TEAEs by maximum intensity
- Incidence of TEAEs by relationship
- Incidence of non-serious TEAEs above reporting threshold of 5% of study participants

Additional summary tables of fatal, serious and discontinuations due to TEAEs by relationship will be produced if more than one of these events occurs.

Summary tables will contain counts of study participant, percentages of study participants in parentheses and the number of events where applicable. A participant who has multiple events in the same SOC and PT during a given treatment will be counted only once in the participant counts for that treatment, but all events will be included.

In summaries including relationship, the following relationships will be summarized: 'Not related', 'Related'. Participants who experience the same event multiple times will be included in the most related category for tabulations by maximum relationship. Events with missing relationship will be considered as 'Related' but recorded as missing in the listings.

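### Crude TEAE percentages cover unequal time at risk when treatments from different periods are compared, and events after PSL stops are charged to PSL in Treatment Period 2 but to CBD later

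*SAP*

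**What the plan says.** SAP Section 11.2 sets two attribution rules. The first is general: "Adverse events will be attributed to the most recent treatment received". The second covers gaps between periods: "Adverse events that occur during the washout periods will be assigned as treatment emergent with regards to the treatment of the previous period". The output is crude: "The number and percentage of participants who experience TEAEs will be summarized by MedDRA SOC, PT and treatment". Section 11.1 adds "Exposure data will be listed only", so no exposure-adjusted rate is planned.

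Tables 3-2 and 3-3 turn the rules into day labels. In Part A, the combination and its placebo control share a single-day row in each of Treatment Periods 4 and 5 (for Treatment Period 4: "4 5 Interaction Phase 5 PSL+Ethanol/PSL+Placebo"). The day after each infusion is labelled PSL. For Day -1 of Treatment Period 3, the Table 3-2 footnote says that if an AE occurs, "then the AE will be summarized where treatment is Ethanol or Placebo since this is the most recent treatment received".

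In Part B, Table 3-3 gives the days between Treatment Periods 4 and 5 to CBD, under a row for CBD dose maintenance, with the footnote "CBD dose maintenance will occur for at least 4 days". The note to protocol Table 1-8 describes the same gap differently: "A washout of at least 4 days will occur between Treatment Periods 4 and 5 for PSL".

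AEs are a secondary endpoint in both parts (SAP Sections 2.1.1 and 2.1.2). SAP Section 2.2.3 names the safety of PSL with and without CBD as an objective of Part B.

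**The concern.** The percentage of participants with at least one event depends on how long they are watched. If one column covers a day and the next covers several, the percentages differ even when the treatments do not. Nothing in the planned output corrects for this.

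The affected comparisons are natural ones. PSL+Ethanol vs Ethanol, PSL+Placebo vs Placebo and CBD+PSL vs PSL are all named PD contrasts in SAP Sections 10.1.2.1 and 10.1.2.2, and readers will look across the AE columns in the same way. In Part B, PSL without CBD is given only in Treatment Period 2. That safety objective therefore has no comparator with a matching window.

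The second issue is consistency. Events in the days after PSL stops count against PSL alone in Treatment Period 2. After Treatment Periods 4 and 5 they leave the CBD+PSL column and go to CBD.

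**Working it through.** **1. Days owned by each column** (phase days in Tables 3-2 and 3-3, excluding follow-up)

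| Part | Column | Days counted | Total |
|---|---|---|---|
| A | PSL+Ethanol | Day 5 or 7 | 1 |
| A | PSL+Placebo | Day 5 or 7 | 1 |
| A | Ethanol or Placebo, given in Treatment Period 1 | Days 1-2 | 2 |
| A | Ethanol or Placebo, given in Treatment Period 2 | Days 3-4, washout 5-6, and Day -1 if it is a separate day | 4 to 5 |
| A | PSL | Days 1-4, 6, 8, 9-10 | 8 |
| B | CBD+PSL | Days 17-23 or 28-34 | 7 |
| B | CBD+Placebo | Days 17-23 or 28-34 | 7 |
| B | PSL | Days 1-8, washout 9-14, and Day -1 if it is a separate day | 14 to 15 |
| B | CBD, excluding Treatment Period 1 | 16 + 4 + 7 | 27 |

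Check: the Part A phases sum to 6 + 10 = 16 days. This agrees with SAP Section 3.2.1 (approximately Day 16) if Day -1 is the last washout day.

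One ambiguity: PSL is dosed again on the evening of Days 5 and 7 (protocol Table 1-3, footnote e). Read literally, the most-recent-treatment rule would then end the PSL+Ethanol window after about 12 h. The one-day figure is the Table 3-2 reading.

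**2. Direction.** A participant with an event in a short window also has one in any longer window that contains it. Lengthening the Ethanol, Placebo or PSL window can therefore only raise its percentage or leave it unchanged. This needs no assumption about hazard.

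**3. Illustrative size.** The documents give no daily AE risk. Assume a constant risk p per day, the same for all treatments, so that incidence over d days is 1 - (1 - p)^d. In Part A, assume half the participants have Ethanol in Treatment Period 1 and half in Treatment Period 2, and average the two incidences.

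At p = 0.10 with the 5-day window: PSL+Ethanol is 10.0%. Ethanol is (19.0% + 41.0%)/2 = 30.0%. The ratio is 0.33.

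| p | Part A: 1 day | 2 days | 4 days | 5 days | Ratio, 2 and 5 days | Ratio, 2 and 4 days |
|---|---|---|---|---|---|---|
| 0.05 | 5.0% | 9.8% | 18.5% | 22.6% | 0.31 | 0.35 |
| 0.10 | 10.0% | 19.0% | 34.4% | 41.0% | 0.33 | 0.37 |
| 0.20 | 20.0% | 36.0% | 59.0% | 67.2% | 0.39 | 0.42 |

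| p | Part B: 7 days | 14 days | 15 days | Ratio, 7 to 14 | Ratio, 7 to 15 |
|---|---|---|---|---|---|
| 0.05 | 30.2% | 51.2% | 53.7% | 0.59 | 0.56 |
| 0.10 | 52.2% | 77.1% | 79.4% | 0.68 | 0.66 |
| 0.20 | 79.0% | 95.6% | 96.5% | 0.83 | 0.82 |

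The true ratio in every row is 1.

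**4. Contrasts within each crossover.** PSL+Ethanol vs PSL+Placebo is 1 vs 1 day, and CBD+PSL vs CBD+Placebo is 7 vs 7 days. Window length cannot bias either.

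**5. Where the extra Part B days come from.** The last PSL dose is on Day 7 in Treatment Period 2 (protocol Table 1-6, footnote h) and in Treatment Periods 4 and 5 (Table 1-8, footnote d). The PSL column's excess over CBD+PSL is 14 - 7 = 7 or 15 - 7 = 8 days, and every one of those days follows the last PSL dose. The matching days after CBD+PSL are in the CBD column.

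**The case against.** A reader might infer that the SAP makes the combinations look safer than they are. The documents do not support that as a general statement. The randomised controls PSL+Placebo and CBD+Placebo have the same windows as the combinations, and PSL+Ethanol vs PSL+Placebo is also the primary PD comparison in Part A. The AE output is descriptive, with no planned test or formal between-treatment safety statement.

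The size is also open. Many of the extra days are undosed washout, and protocol Section 4.2.1 reports better PSL tolerability after 2 to 3 days of repeated dosing. If events cluster around dosing, the added days contribute few and the ratios move towards 1. This limits the size, not the direction.

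A flat contradiction over Days 24 to 27 would also be too strong a reading. CBD is dosed on those days, so it is literally the most recent treatment, and Table 3-3 does not label the row a washout. Only the protocol note does, and only for PSL. Nor does the text on sudden discontinuation in protocol Section 7.1.3 show a particular hazard here: it concerns a study hold, and the PSL step-down days in Treatment Periods 4 and 5 stay with CBD+PSL.

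The listings carry onset date and time, time to onset and relationship, so single events can be traced. That does not make the tabulated percentages comparable.

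Equal windows have limits too. A 24 h window in Part A mainly shortens Ethanol and Placebo and recovers few next-day events. In Part B, windows of equal length do not have equal background CBD. Both points are fair and call for footnotes.

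**Conclusion.** The point holds for comparisons between periods. PSL+Ethanol is counted over 1 phase day against 2 to 5 for Ethanol, PSL+Placebo over 1 against 2 to 5 for Placebo, and CBD+PSL over 7 against 14 to 15 for PSL alone. Relative to an equal-window count, the longer windows raise the comparator's percentage or leave it unchanged. The documents do not allow the amount to be estimated. The illustrative ratios (0.31 to 0.42 in Part A, 0.56 to 0.83 in Part B) rest on an assumed constant and equal daily risk of 5% to 20% and are not predictions.

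The two contrasts within the randomised crossovers are sound as regards window length.

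The attribution of events after PSL stops is inconsistent between Treatment Period 2 and Treatment Periods 4 and 5. For Days 24 to 27 the SAP washout rule, Table 3-3 and protocol Table 1-8 need to be reconciled. Because AEs are a secondary endpoint and the remedy is cheap, the change should be made, although it does not threaten the primary analyses.

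**What to change.** Keep the current tables as the overall display and add supplementary TEAE tables with equal onset windows.

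- **Part A:** onset from infusion start to 24 h later in each of Treatment Periods 1, 2, 4 and 5, regardless of the evening PSL dose.
- **Part B:** onset from the first PSL/placebo dose to 4 days after the last one in each of Treatment Periods 2, 4 and 5, about 7 + 4 = 11 days each. This fits the minimum gaps of 6 days after Treatment Period 2 and 4 days after Treatment Period 4. Footnote that the post-dose days fall on no CBD, CBD maintenance and CBD taper respectively.
- **All TEAE tables:** state person-days at risk in each treatment column, and name PSL+Placebo and CBD+Placebo as the matched-window comparators.
- **Attribution text:** reconcile Section 11.2, Table 3-3 and protocol Table 1-8 for Days 24 to 27. State whether the evening PSL dose on Days 5 and 7 in Part A ends the combination's window.

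The cost is SAP wording and a few extra tables, since onset date and time are already part of the planned listings. The downside is that late-onset events appear only in the overall tables.

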3 OBJECTIVES AND ENDPOINTS

The objectives and corresponding endpoints for this study are presented in [Table 3-1](#).

Table 3-1: Study objectives and endpoints

Objectives	Endpoints
Primary	

 Part A: To evaluate the PD interaction between steady-state treatment with PSL and ethanol 	
 Smooth pursuit (%) to assess eye movement coordination and attention

 Part B: To evaluate the PK interaction between steady-state treatment with PSL and CBD 	
 $C_{max,ss}$ and AUC_{τ} obtained from the plasma concentration-time profiles for PSL and CBD
Secondary	

 Part A: To evaluate the PK interaction between steady-state treatment with PSL and ethanol 	
 Ethanol dose infused over time $C_{max,ss}$ and AUC_{τ} obtained from the plasma concentration-time profiles for PSL

 Part B: To evaluate the PK interaction between steady-state treatment with PSL and CBD 	
 $t_{1/2}$, and $CL_{ss/F}$ obtained from the plasma concentration-time profiles for PSL and CBD

 Parts A and B: To evaluate the PD interaction between steady-state treatment with PSL and ethanol or between steady-state treatment with PSL and CBD 	
 Smooth pursuit (%) to assess eye movement coordination and attention (Part B only) Saccadic peak velocity (degrees/sec) to assess sedation Adaptive tracking (%) to assess visuo-motor control and vigilance Body Sway to assess postural stability

 Parts A and B: To evaluate the safety and tolerability of PSL in study participants receiving concomitant ethanol or CBD 	
 Adverse events (AEs), serious adverse events (SAEs), treatment-related AEs, and AEs leading to discontinuation of the study
Other	

 Parts A and B: To evaluate the safety and tolerability of PSL in study participants receiving concomitant ethanol or CBD 	
 Vital signs (pulse rate, respiratory rate, systolic blood pressure [SBP], and diastolic blood pressure [DBP]) 12-lead electrocardiogram (ECG) parameters Physical examination findings Clinical laboratory test results (hematology, clinical chemistry, and urinalysis)

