9.6 Planned safety analyses

All safety analyses will be performed using the FAS. All safety variables will be listed and summarized by each study part and treatment.

All AEs will be coded using the Medical Dictionary for Regulatory Activities (MedDRA[®]) and characterized as pretreatment and treatment-emergent according to the intake of the IMP. All AE data will be listed by study participant number, visit, treatment and time. The listings will include the following data pertaining to the AEs: start and end dates with relative days to study medication administration, duration, intensity, seriousness, relationship to study medication, action taken, and final outcome.

The occurrence and incidence of TEAEs will be summarized by study part according to the intake of PSL (pretreatment or treatment-emergent) and by intensity or relationship to PSL, CBD and ethanol.

Safety laboratory measurements, vital signs and 12-lead ECGs parameters will be tabulated by study part and treatment using descriptive statistics. Laboratory values outside the reference range will be flagged in the listings. Any PDILI events will be listed.

Assessment of suicidality will be listed.

Physical examinations abnormalities and psychological and mental status abnormalities will be listed.

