10.3.3 Recording and follow up of AE and/or SAE

AE and SAE Recording

- When an AE/SAE occurs, it is the responsibility of the Investigator to review all documentation (eg, hospital progress notes, laboratory reports, and diagnostics reports) related to the event.
- The Investigator will then record all relevant AE/SAE information in the eCRF.
- It is **not** acceptable for the Investigator to send photocopies of the participant's medical records to UCB in lieu of completion of the UCB AE/SAE eCRF page.
- There may be instances when copies of medical records for certain cases are requested by UCB. In this case, all participant identifiers, with the exception of the participant number, will be redacted on the copies of the medical records before submission to UCB.
- The Investigator will attempt to establish a diagnosis of the event based on signs, symptoms, and/or other clinical information. Whenever possible, the diagnosis (not the individual signs/symptoms) will be documented as the AE/SAE.

Assessment of Intensity

The Investigator will make an assessment of intensity for each AE and SAE reported during the study and assign it to 1 of the following categories:

- Mild: An event that is easily tolerated by the participant, causing minimal discomfort and not interfering with everyday activities.
- Moderate: An event that causes sufficient discomfort and interferes with normal everyday activities.
- Severe: An event that prevents normal everyday activities. An AE that is assessed as severe should not be confused with a SAE. Severe is a category utilized for rating the intensity of an event; and both AEs and SAEs can be assessed as severe.
- An event is defined as 'serious' when it meets at least 1 of the predefined outcomes as described in the definition of an SAE, NOT when it is rated as severe (eg, a severe AE may be either serious or not serious, depending on whether these criteria are also met).

The National Cancer Institute Common Terminology Criteria for Adverse Events (NCI-CTCAE) should be used as a supportive standardization instrument to evaluate AEs and SAEs but the final intensity grading by the Investigator must be mild, moderate, or severe.

Assessment of Causality

- The Investigator is obligated to assess the relationship between study medication and each occurrence of each AE/SAE.

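### SAP 11.2 summarises related adverse events without naming the agent, although Protocol 9.6 plans relationship to PSL, CBD and ethanol, and SAP 3.9 declares no change

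*SAP*

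**What the plan says.** Protocol section 3, Table 3-1, sets a secondary safety endpoint for both parts that includes "treatment-related AEs, and AEs leading to discontinuation of the study". The objective it serves is the safety and tolerability of PSL in people also receiving ethanol or CBD. SAP 2.1.1 and 2.1.2 carry the same endpoint.

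Protocol 9.6 plans to summarise TEAEs by study part "and by intensity or relationship to PSL, CBD and ethanol". For the adverse event listing, the same section names no agent and asks only for "relationship to study medication, action taken, and final outcome". Protocol 10.3.3 describes causality in the same undivided way: "The Investigator is obligated to assess the relationship between study medication and each occurrence of each AE/SAE".

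SAP 11.2 plans one incidence table by relationship. It says "In summaries including relationship, the following relationships will be summarized", and the two levels it then gives are *Not related* and *Related*. Its overview table has one row of this kind, within "drug-related TEAEs, severe TEAEs and TEAEs leading to death". Neither place says which agent is meant. Events with missing relationship are counted as related. TEAEs are tabulated by system organ class (SOC), preferred term (PT) and treatment, and each event goes to the most recent treatment received.

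SAP 3.9, the list of changes from the protocol, has no entry on relationship. SAP 1 says that the protocol's analysis stands unless the SAP specifies otherwise.

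**The concern.** Each combination treatment contains two agents that could cause an adverse event. Protocol Table 6-1 lists PSL, ethanol and CBD all as study treatments, so an investigator could judge an event related to study medication because of any of them. Protocol 9.6 meets this by naming the three agents. If the SAP reduces relationship to two levels with no agent, a reader of the PSL+Ethanol column sees how many participants had a related event but not what it was related to.

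What is at stake is the interpretation of a named secondary endpoint whose objective concerns PSL. Causality per agent is also hard to reconstruct after the fact, so the point is best settled before the data are final.

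**Working it through.** The documents state no adverse event rate, so no arithmetic on rates applies. The check sets the texts side by side and traces where events fall.

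1. **Relationship categories.** Protocol 9.6 names three agents. SAP 11.2 gives two levels, one overview row and one relationship table, and its listings carry one relationship item. No agent is named in any of these. Read naturally, this is a single classification.

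2. **Does the fallback in SAP 1 restore the split?** Not clearly. It keeps the protocol's analysis only where the SAP does not specify something else, and SAP 11.2 does specify the relationship summaries. A programmer working from SAP 11.2 would build two categories, not two per agent.

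3. **Was the change declared?** SAP 3.9 goes down to the level of adding trough concentrations as a parameter, but does not mention relationship.

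4. **Where Part A events are tabulated (SAP Table 3-2).**
   - Treatment Periods 1 and 2: Ethanol or Placebo.
   - Days 5 and 7: PSL+Ethanol or PSL+Placebo.
   - Days 1 to 4, 6 and 8 to 10: PSL.

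   Intoxication on a clamp day is therefore tabulated under Ethanol or PSL+Ethanol, not under PSL. The exception is an ethanol after-effect that starts the day after a clamp. Days 6 and 8 carry the PSL label, so such an event goes under PSL. Of the 4 + 1 + 3 = 8 days labelled PSL, each participant has only one that follows an ethanol clamp, because every sequence in SAP 2.2.2 gives ethanol in just one of Treatment Periods 4 and 5.

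5. **Where Part B events are tabulated (SAP Table 3-3).** Events in Treatment Periods 4 and 5 go under CBD+PSL or CBD+Placebo. The combination column mixes two possible causes in the same way as PSL+Ethanol.

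6. **What the treatment column can and cannot do.** It shows what the participant had received. It does not show which agent the investigator held responsible. In PSL+Ethanol and CBD+PSL, and for Day 6 or 8 after-effects under PSL, the plan as written leaves that open. The rule that counts missing relationship as related adds events to the same undivided category.

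**The case against.** The strongest reply is that a single classification is inferred, not stated. SAP 11.2 gives the response levels without saying whether they are applied once or per agent. The eCRF and table shells are not among the documents. The silence of SAP 3.9 fits an intention to change nothing. The protocol itself is uneven: its listing and its causality instruction speak only of study medication. If the causality question refers to PSL alone, an event due only to ethanol would be classed as not related. The endpoint is worded as treatment-related, and a count related to any treatment meets that wording.

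Much of this stands as a limit on the claim. None of it supplies the missing agent. Under each of these readings SAP 11.2 still fails to say what an event is related to, while Protocol 9.6 names three agents for the summaries.

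A reader might go further and infer that ethanol intoxication on clamp days inflates the drug-related count in tables of PSL safety. The documents do not support this. TEAEs are shown by treatment, there is no pooled PSL table, and clamp-day events fall under Ethanol or PSL+Ethanol. Nor does the endpoint become uninformative about PSL. PSL+Ethanol against Ethanol, descriptive and subject to period order, shows what PSL adds. In Part B, CBD+PSL against CBD+Placebo does so within the randomised crossover.

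Counting missing relationship as related is a conservative rule and not itself a fault. It only needs to be stated per agent.

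**Conclusion.** The concern holds in a limited form. Followed as written, SAP 11.2 drops a breakdown that Protocol 9.6 plans for a secondary endpoint, and SAP 3.9 does not say so. Related events under PSL+Ethanol and CBD+PSL cannot be assigned to one agent, and neither can ethanol after-effects that start on Part A Day 6 or 8 and are tabulated under PSL.

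The loss is one of attribution, in descriptive safety tables in both parts. No primary endpoint or hypothesis test is touched, and total TEAEs by treatment remain interpretable. The size cannot be given as a number, because the documents contain no rate of related events and do not show how the eCRF asks about causality.

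The conclusion rests on two readings: that naming three agents in Protocol 9.6 means a summary for each, and that the unnamed levels in SAP 11.2 would be programmed once. Both are the natural reading, but neither is explicit. The change is worth making before the data are final.

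**What to change.** In SAP 11.2:

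- Replace the single drug-related overview row with rows for related to PSL, related to ethanol (Part A) or CBD (Part B), and related to any of these.
- Produce the SOC and PT relationship table on the same per-agent basis.
- Apply the missing-relationship rule separately for each agent.

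Confirm that the eCRF records causality per agent, and add a field if it does not and collection still allows it. If per-agent causality is not recorded, state in SAP 3.9 that the summary departs from Protocol 9.6, and justify it.

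The cost is a few extra table rows, some SAP wording and possibly one eCRF field.
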